2.5. Statistical Assessment of the Trial Objectives

2.5.1. Primary Endpoint

Hypothesis testing will be performed for the primary endpoint: change in frequency of migraine days (Weeks 1-12). This endpoint will be calculated as outlined in Section 2.2.2 and will utilize the missing data rules provided in Section 2.7.2. Summary statistics including confidence intervals for the treatment differences will be used to summarize the results for the primary endpoint. Testing will also be employed. The hypotheses tested are

$$H_0: \Delta_{\text{plb}} = \Delta_{403} \qquad H_a: \Delta_{\text{plb}} \neq \Delta_{403}$$

where Δ_{403} is the change in migraine days for subjects in the ALD403 treatment arm and Δ_{plb} is similarly defined for the placebo subjects. The change from baseline is expected to be negative as migraines are being reduced. While the test outlined above is two sided, as is the alpha level used for this study (i.e. 5%), clinically relevant results require a larger reduction of migraines on the ALD403 arms.

An ANCOVA model will be used to test for a difference between treatment arms. This model will include the change from baseline measure as the response variable. Treatment and variables measuring the stratification factors concepts: baseline migraine days (continuous covariate) and prophylactic medication use (binary covariate: use vs. no use) will be the independent variables.

2.5.2. Key Secondary Efficacy Analyses

Summary statistics including confidence intervals for the treatment differences will be used to summarize the results for the key secondary endpoints. Testing, as outlined below, will be used for the key secondary endpoints.

Responder Rates

Testing of the 75% migraine responder rate (Weeks 1-4), 75% migraine responder rate (Weeks 1-12) and 50% migraine responder rate (Weeks 1-12) endpoints will be performed with a CMH test controlling for the randomization stratification factors baseline migraine days (<17 days, \geq 17 days) and prophylactic medication use (use vs. no use). Cumulative distribution of the responder rate will be plotted.

Percentage of Subjects with a Migraine on the Day after Dosing

The percent of subjects with a migraine on the day after dosing key secondary endpoint will be tested with a stratified extended CMH test.⁴ Randomization stratification factors baseline migraine days (<17 days, \geq 17 days) and prophylactic medication use (use vs. no use) will be used for this test. An extended CMH test is used here as subjects with missing data will have a value imputed between 0 and 1 as outlined in Section 2.7.2.

Reduction in Migraine Prevalence from Baseline to Week 4

The reduction in migraine prevalence from baseline to Week 4 endpoint will be the difference in daily prevalence rates between Week 1 and baseline, Week 2 and baseline, etc. The treatment effect will be tested using a repeated-measures approach (Mallinckrodt and Lipkovich, 2016),⁵

using the subject level change in migraine rate (see Section 2.2.2) for Weeks 1, 2, 3 and 4 as the outcome variable. The model will specify an unstructured variance/covariance matrix and include the treatment group, week, baseline value of the outcome variable and with treatment group-by-week interaction. The Kenward-Roger approximation will be used to estimate the degrees of freedom.

Headache Impact Test (HIT-6)

The change in HIT-6 total score will be tested using an ANCOVA model similar to the one used for the primary endpoint. This model will include the HIT-6 change from baseline at Week 12 as the response variable. Treatment and the stratification factors will be the independent variables.

Acute Migraine Medication Usage

The change in acute migraine medication usage between baseline and Weeks 1-12 will be tested using an ANCOVA model similar to the one used for the primary endpoint. This model will include the acute migraine medication usage change from baseline as the response variable. Treatment and the stratification factors will be the independent variables.

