13.4.2. Efficacy Analyses

Efficacy endpoints will be summarized with descriptive statistics. The migraine and headache endpoints will be summarized by 4, 12, and 24 week intervals with the remaining endpoints being summarized by study week.

Primary Efficacy Analyses

Hypothesis testing will be performed for the primary endpoint: change in frequency of migraine days (Weeks 1-12). This endpoint will be calculated as outlined in Section 12.1.2 and will utilize the missing data rules provided in Section 13.3.2. Summary statistics including confidence intervals for the treatment differences will be used to summarize the results for the primary endpoint. Testing will also be employed. The hypotheses tested are

$$H_0: \Delta_{\text{plb}} = \Delta_{403}$$

$$H_a: \Delta_{\text{plb}} \neq \Delta_{403}$$

where Δ_{403} is the change in migraine days for subjects in the ALD403 treatment arm and Δ_{plb} is similarly defined for the placebo subjects. The change from baseline is expected to be negative as migraines are being reduced. While the test outlined above is two sided, as is the alpha level used for this study (i.e. 5%), clinically relevant results require a larger reduction of migraines on the ALD403 arms.

An ANCOVA model will be used to test for a difference between treatment arms. This model will include the change from baseline measure as the response variable. Treatment and the stratification variables: baseline migraine days (continuous predictor) and prophylactic medication use (use vs. no use) will be the independent variables.

Secondary Efficacy Analyses

Summary statistics including confidence interval for the treatment differences will be used to summarize the results for the secondary endpoints. Testing will be used for the key secondary endpoints. A CMH test controlling for the randomization stratification factors will be used for the responder rate key secondary endpoints, and the percent of subjects with a migraine on the day after dosing endpoint will be tested with an extended CMH test.¹⁵

The acute migraine medication day endpoint will be tested using an ANCOVA model similar to the one used for the primary endpoint. The time to first migraine analysis will be descriptively summarized based upon Kaplan-Meier methods.

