The missing data rules provided in Section 13.3.2 will be used for the key secondary endpoints, except for the percentage (prevalence) of subjects with a migraine on the day after dosing endpoint. Subjects who did not complete the eDiary on the day following dosing will be included in the prevalence rate calculation based upon their Week 1-4 daily migraine rate. Hence, subjects with a migraine will be included in the rate calculation as a value of 1, subjects who completed the eDiary and did not have a migraine will be included as a 0, and subjects who did not complete the eDiary will be included with a value between 0 and 1 equal to their prevalence rate in Weeks 1-4 (i.e. the number of Weeks 1-4 migraine days divided by 28). The reduction in migraine prevalence from baseline to Week 4 endpoint will be difference in daily prevalence rates between Week 1 and baseline, Week 2 and baseline, and so on. The baseline daily prevalence will be calculated as the number of migraine days in baseline divided by 28. The Week 1 daily prevalence will be the number of migraine days in Week 1 divided by 7, with a similar definition for Weeks 2, 3, and 4. The same missing data approach for the day after dosing endpoint will be used for these weekly measures (i.e. any day the subject does not complete the diary will be assigned a value equal to the Weeks 1-4 prevalence rate). The treatment effect will be evaluated using a repeated-measures approach.¹⁶ The model will specify an unstructured variance/covariance matrix and include the treatment group, visit, baseline value of the outcome variable and treatment group-by-visit interaction. The Kenward-Roger approximation will be used to estimate the degrees of freedom. Pharmacokinetic Analyses

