3.2. Definition of Baseline

Baseline assessment for migraine and headache endpoints will be based upon the data recorded in the headache eDiary during the 28 days following screening. For other variables, the baseline assessment will be the latest available valid measurement taken prior to the administration of Investigational Product. This will generally be Day 0.

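### The ANCOVAs for the key secondary HIT-6 and acute-medication endpoints do not name the outcome's own baseline as a covariate; naming it costs nothing and would probably gain precision

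*SAP*

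**What the plan says.** The primary ANCOVA (SAP 2.5.1) has treatment plus "baseline migraine days (continuous covariate) and prophylactic medication use (binary covariate: use vs. no use) will be the independent variables". Its response is change in migraine days, so the first covariate does two jobs: it stands for a stratification factor and it is the outcome's own baseline.

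For HIT-6, SAP 2.5.2 opens with "The change in HIT-6 total score will be tested using an ANCOVA model similar to the one used for the primary endpoint" and then specifies "HIT-6 change from baseline at Week 12 as the response variable. Treatment and the stratification factors will be the independent variables". For acute migraine medication it opens with an equivalent sentence and then specifies "acute migraine medication usage change from baseline as the response variable. Treatment and the stratification factors will be the independent variables". SAP 1.3 gives the stratification factors as screening migraine days (<17 vs ≥17) and prophylactic medication use. Protocol 13.4.2 says "The acute migraine medication day endpoint will be tested using an ANCOVA model similar to the one used for the primary endpoint" and gives no covariate list.

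In the same SAP section, the repeated-measures model for migraine prevalence does name the term: it will "include the treatment group, week, baseline value of the outcome variable and with treatment group-by-week interaction". Protocol 13.4.2 has matching wording ("include the treatment group, visit, baseline value of the outcome variable and treatment group-by-visit interaction").

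Both endpoints are under multiplicity control as Key Secondary #5 (SAP 2.3, Table 2), for 300 mg only, with Holm thresholds 0.025 and 0.05.

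**The concern.** When the list is carried from the primary model to the other two endpoints, migraine days keeps its role as a stratification factor but is no longer the outcome's baseline. Nothing in the list takes over that role. An analysis of change without the own baseline is usually less precise than one with it, because subjects with extreme baseline values tend to move back toward the mean and the model leaves that variation in the error term.

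The wording is also open to more than one reading. A programmer could fit the list as written, or could read the reference to the primary model as bringing in an own-baseline term. The list does not say whether migraine days enters as continuous, as in SAP 2.5.1, or as <17 vs ≥17, as in the CMH paragraphs of 2.5.2. So the covariate set of two confirmatory tests could be settled at programming.

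A smaller point of the same kind: the prevalence repeated-measures model (SAP 2.5.2, Protocol 13.4.2) and the repeated-measures sensitivity models (SAP 2.7.3) leave out prophylactic use, which the primary model includes.

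**Working it through.** **The plan's own figures.** SAP 1.5 gives power only for the primary and the 75% responder endpoints. For the primary endpoint, 350 per arm, a difference of 1 day and SD 4 give 1 / (4 × √(2/350)) = 3.307, and Φ(3.307 − 1.960) = 91.1%, which agrees with the stated 90% or more. For 20% vs 31% responders the power is 91.8%, against 90% stated. There is no stated SD, correlation or power for HIT-6 or medication days, so everything below rests on assumptions.

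**Assumptions.**
- The own baseline has SD 1 and the follow-up value has SD k.
- ρ is the correlation of own baseline with follow-up, taken as 0.3 to 0.8.
- r is the correlation of own baseline with baseline migraine days, taken as 0 to 0.4.
- Migraine days relates to follow-up only through the own baseline.

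**Formulas.**
- Residual variance of the change score, as listed (migraine days in the model): 1 + k² − 2ρk − [r(1 − kρ)]²
- Residual variance with own baseline added: k²(1 − ρ²)
- For k = 1 the ratio of the second to the first is (1 + ρ) / (2 − r²(1 − ρ)).
- The CI width ratio is the square root of the variance ratio R.
- Power, if the listed model has 80%: Φ((z₁₋α/₂ + 0.842)/√R − z₁₋α/₂)

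**Equal SDs (k = 1).**

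| ρ | r | As listed | With own baseline | R | CI width | Power, α 0.05 | Power, α 0.025 |
|---|---|---|---|---|---|---|---|
| 0.3 | 0 | 1.400 | 0.910 | 0.650 | 0.81 | 93.5% | 94.3% |
| 0.5 | 0.4 | 0.960 | 0.750 | 0.781 | 0.88 | 88.7% | 89.4% |
| 0.8 | 0.4 | 0.394 | 0.360 | 0.915 | 0.96 | 83.4% | 83.7% |

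In the middle row, 350 per arm works like 350/0.781 ≈ 448.

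**Unequal SDs (r = 0, from 80% power at α 0.05).**

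| k | ρ | R | Power |
|---|---|---|---|
| 0.8 | 0.3 | 0.502 | 97.7% |
| 1.25 | 0.3 | 0.785 | 89% |
| 1.25 | 0.5 | 0.893 | 84% |
| 1.25 | 0.8 | 1.000 | 80% |
| 1.5 | 0.3 | 0.871 | 85% |
| 1.5 | 0.5 | 0.964 | 81% |

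The gain vanishes where kρ = 1, because the change score is then uncorrelated with the own baseline. Over k = 0.8 to 1.5, R runs from 0.502 to 1.000.

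**Checks.** A different correlation structure, with migraine days correlated 0.5 with the own baseline and 0.3 with follow-up, gives R of 0.65, 0.78 and 0.91 for ρ = 0.3, 0.5 and 0.7. In a simulation with 350 per arm and 4,000 runs (ρ = 0.5, correlations 0.3 and 0.2 with migraine days, α 0.025), power rose from 80.1% to 90.1%. Type I error was 2.7% as listed and 2.6% with the own baseline.

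**Prophylactic use in the prevalence model.** With an assumed partial R² of 5%, R = 0.95 and power goes from 80.0% to 82.0%.

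**The case against.** - **The reference to the primary model may already supply the term.** In that model the continuous covariate is the outcome's own baseline, so a programmer could reasonably carry the idea over. This stands as a possible intention. It does not settle the model: copying the primary model literally brings in migraine days, a specific list follows that omits the term, and the same section names the term where it is wanted.
- **The primary model also settles the form of migraine days.** It enters the primary ANCOVA as continuous, and the <17/≥17 split belongs to the CMH tests. This is a fair reading, and what remains is a small ambiguity.
- **The gain may be nil.** This stands. Nothing in the documents supports equal SDs or any particular correlation, and at k = 1.25 with ρ = 0.8 the gain is zero.
- **Position in the sequence.** Key Secondary #5 is reached only if twelve earlier tests all succeed (1 + 3 + 2 for 300 mg, then 1 + 3 + 2 for 100 mg). The power figures above are therefore conditional on reaching it, and the unconditional gain is smaller by an unknown factor.
- **Prophylactic use in the other models is a side issue.** Agreed. Those models already contain the relevant baseline, and the addition is optional.

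None of this argues for leaving the covariate list as it is. Whether or not the sponsor already intends the term, the same sentence resolves the matter.

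**Conclusion.** The point holds as a low-priority improvement. As written, neither model names its outcome's own baseline. The listed analyses are valid and no other test depends on them, so the trial's main conclusions are not at risk.

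The likely benefit is a residual variance of 0.65 to 0.915 of the listed model and a confidence interval 4% to 19% narrower, assuming equal SDs, ρ of 0.3 to 0.8 and r of 0 to 0.4. If the SD ratio lies anywhere from 0.8 to 1.5, the variance ratio is between 0.50 and 1.00. It is firm that the term is not named. The size of the gain cannot be fixed from the documents.

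**What to change.** In SAP 2.5.2, write out both models:

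- **HIT-6 change at Week 12:** treatment, baseline HIT-6 total score, baseline migraine days (continuous), prophylactic medication use.
- **Acute-medication change, Weeks 1-12:** treatment, baseline acute-medication days, baseline migraine days (continuous), prophylactic medication use.

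Optionally, add prophylactic use to the prevalence repeated-measures model and to the repeated-measures models in SAP 2.7.3, so that they match the primary model.

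The cost is SAP wording only, with no added patients, visits or alpha. HIT-6 is collected at screening and Day 0, and SAP 3.2 already defines its baseline ("the baseline assessment will be the latest available valid measurement taken prior to the administration of Investigational Product"). Medication use is recorded in the eDiary from screening, and Table 4 fixes its baseline interval. A subject with a change score necessarily has the baseline value, so the new covariate excludes nobody. The change should be made before the unblinding for the primary analysis at Week 12 (SAP 1.4), so that the covariates are not chosen with treatment assignments known.

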2.5.3. Secondary Efficacy Analyses

Summary statistics will be used to summarize the results for the secondary endpoints. The time to first migraine analysis will be descriptively summarized based upon Kaplan-Meier methods, see Section 3.4.2.3. Testing of the Weeks 1-24 change from baseline in migraine days will be performed using a test identical to the test used for the primary endpoint.

2.5.4. Tertiary Efficacy Analyses

Tertiary endpoints will be summarized with descriptive statistics by treatment group. For the Migraine Free Days endpoint the summary measures will be the longest migraine free interval that started within the first two weeks following treatment.

2.6. Safety Analyses

Safety endpoints will be summarized with descriptive statistics. All safety summaries and analyses will be performed using the safety population.

Prior and Concomitant medications will be coded by the World Health Organization (WHO) Drug Dictionary version September 2012.

Adverse Events and Medical History will be coded using MedDRA version 20.1.

2.7. Additional Statistical Analyses

2.7.1. Adjustments for Covariates and Examination of Subgroup Analyses

Summaries with descriptive statistics and frequency counts on the primary endpoint for both dose groups will be provided for the subgroups indicated below. Forest plots will also be created for subgroup analyses and will display treatment differences. The subgroups will be

- Calculated baseline migraine days (<17 days vs. \geq 17 days)
- Prophylactic medication use vs. no prophylactic medication use (based upon a medical review of medications)
- Sex
- Race (groups with minimal subjects will be combined)
- Age Group (\leq 35 yrs, >35 yrs)
- Age Group at Diagnosis of Migraine (\leq 21 yrs, >21 yrs)
- Duration of Migraine at Baseline (\leq 15 yrs, >15 yrs)
- Baseline Medication Overuse (MOH, no MOH)
- Baseline Triptan use (\geq 33% of days, <33% of days)

2.7.2. Handling of Dropouts or Missing Data

Summary statistics will be reported based upon observed data except for the imputation outlined below. Additionally, if the start date of an AE or concomitant medication is incomplete or missing, it will be assumed to have occurred on or after the infusion of trial medication, except if an incomplete date (e.g., month and year) clearly indicates that the event started prior to treatment.

Subjects who do not complete the eDiary daily will have missing data. It is expected that most missing diary data will be sporadic.

Missing Headache End Date and Time

If the end date and time for a headache recorded in the eDiary is missing the headache end date will be set to the earlier of 23:59 on the day before the next reported headache or 23:59 on the last entry reported into the diary (i.e. the last evening report or if no evening report was completed after the start of the headache 23:59 on the day the headache started). Headaches that are not reported as stopped by the subject are missing the answers to the questions that allow for the determination of whether the headache was a migraine or not. In this population most headaches are migraines. Hence, these headaches with missing 'end' information will be classified as migraines.

Missing Data Rule 1

If the eDiary has been completed at least 21 days in a 28 day interval, then a normalization procedure will be used. The results will be normalized to 28 days by multiplying the observed results by the inverse of the completion rate (e.g. if a subject does not complete the eDiary on 5 days they will have completed the diary on 82% of the days and the normalized results will be the observed results times 1.22).

For the tertiary endpoints (except migraine free days), only Missing Data Rule 1 will be used and the denominators for will reflect the number of subjects who completed the eDiary 21 or more days in the 28 day interval. For Migraine Free Days no imputation will be used.

Missing Data Rule 2

If the eDiary has been completed on less than 21 days in the 28 day interval then the results for the 28 day interval will be a weighted function of the observed data for the current four week interval and the results from the previous interval. The weights will be proportional to how many days the diary was completed and will provide greater weight for higher completion rates. Specifically, the results will be derived as

$$28 (W X_c + (1 - W) X_p),$$

where W is the number of days the diary was completed/20, X_c is the available average daily results for the current interval and X_p are the average imputed daily results for the previous interval.

Missing Data Rule for Prevalence Endpoints.

For the percentage (prevalence) of subjects with a migraine on the day after dosing and reduction in migraine prevalence from baseline to Week 4 endpoints subjects who did not complete the eDiary on any day following dosing will be included in the calculation based upon their Week 1-4 daily migraine rate. Hence, subjects with a migraine on a given day will have a rate of 1 for that day, subjects who completed the eDiary and did not have a migraine will be included as a 0, and subjects who did not complete the eDiary will be included with a value between 0 and 1 equal to their prevalence rate in Weeks 1-4 (i.e. the number of Weeks 1-4 migraine days divided by 28).

Missing Data Rule for HIT-6

If a subject does not complete the HIT-6 at week 12 their Week 12 change from baseline result will be set to imputed values using LOCF. This imputation will only be performed at Week 12.

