2.2. Clinical Trial Endpoints

The efficacy, safety, pharmacokinetic and immunogenicity of ALD403 will be assessed using the following endpoints. Greater detail concerning these endpoints can be found in Section [2.2.2](#).

Primary Efficacy Endpoint

- Change in frequency of migraine days (Weeks 1-12)

Key Secondary Efficacy Endpoints

- 75% migraine responder rate (Weeks 1-4)
- 75% migraine responder rate (Weeks 1-12)
- 50% migraine responder rate (Weeks 1-12)
- Percentage of subjects with a migraine on the day after dosing
- Reduction in migraine prevalence from baseline to Week 4
- Headache Impact Test (HIT-6)
- Acute Migraine Medication Usage

Other Secondary Efficacy Endpoints

- Headaches/migraines with acute medication usage
- Change in frequency of migraine days (Weeks 1-24)
- 100% migraine responder rate (Weeks 1-12)
- Migraine responder rates for time periods other than Weeks 1-12

- Change in frequency of migraine days between baseline and time periods other than Weeks 1-12
- Headache responder rates
- Change in the frequency of headache days
- Percent change in headache or migraine days
- Time to first migraine after dosing
- Headache/migraine hours
- Headache/migraines with severe intensity
- Patient Global Impression of Change (PGIC)
- Short-Form Health Survey (SF-36 v 2.0)
- Health-Related Quality of Life (EQ-5D-5L)

Tertiary Endpoints

- Headache episodes/migraine attacks
- Migraine symptom-free days
- Most Bothersome Symptom (MBS)
- Migraine Free Days

Safety Endpoints

- Adverse events (AEs) and serious adverse events (SAEs)
- Clinical laboratory assessments
- Vital signs
- Electrocardiograms (ECGs)
- Columbia-Suicide Severity Rating Scale (C-SSRS)

Pharmacokinetic Endpoints

- Free ALD403 plasma concentrations

Immunogenicity Endpoints

- Development of specific anti-ALD403 antibodies
- Characterization of specific anti-ALD403 antibodies for neutralizing activity

2.2.1. eDiary

Subjects will complete a daily headache eDiary from the time of screening to Week 24. The diary includes two separate functionalities. The evening report is completed each trial day whether or not the subject had a headache. Among other items this evening report is where

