subjects record if they took acute migraine medication on that day. In addition to the evening report the eDiary captures headaches as individual events with a start and end time. It is these headache reports which are used to derive the migraine and headache endpoints. Subjects are allowed to tell the eDiary about headaches that started today and yesterday and are unable to record headaches that started before yesterday. Headaches must be entered in order and at the completion of the headache the subject answers questions about the headache that allow the headache to be classified as a migraine or non-migraine headache as outlined in Section 2.2.2. The eDiary data from the 28 days following screening visit will be used to determine eligibility criteria, and the baseline migraine and headache results.

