2.2.2. Migraine and Headache Endpoints

In the statistical analysis plan the term headache will encompass both headaches and migraine headaches. Migraine headaches (migraines) are a subgroup of the headaches with the characteristics outlined below. In this way all migraines are headaches but not all headaches are migraines. Migraine and headache data will be collected through Week 24. Headaches (i.e. headache episodes) will be self-reported by the subject. An episode is a single headache event which lasts at least 30 minutes, as defined by the subject reported start and end time. Start and end times are recorded in 15 minute intervals (e.g. 4:00, 4:15, 4:30, ...). The migraine and headache endpoints will be summarized in four week, twelve week and the twenty-four week intervals. Specifically, migraine and headache endpoints will be summarized for the four week intervals: Weeks 1-4, 5-8, 9-12, 13-16, 17-20, 21-24, the twelve week intervals 1-12, 13-24, and Weeks 1-24 as outlined in Section 2.3 . The results from Weeks 1 to 12 will be used for the primary analysis.

Migraine Day

A migraine day is defined as any day with a headache that meets the chronic migraine definition as outlined in the International Headache Society (IHS) International Classification of Headache Disorders (ICHD, 3rd edition, beta version 2013), Section 1.3 with diagnostic criteria C limited to items 1 and 3.¹ Criteria C defines what characteristics must be present for a headache to be considered a migraine. These characteristics define a migraine as a self-reported headache that:

1. Lasted
 - a. 4 hours or more **or**
 - b. 30 minutes to 4 hours, and believed by the subject to be a migraine that was relieved by medication
2. Had at least 2 of the following:
 - a. Unilateral location
 - b. Pulsating quality
 - c. Moderate or severe pain intensity
 - d. Aggravation by or causing avoidance of routine physical activity
3. Had at least 1 of the following
 - a. Nausea and/or vomiting
 - b. Photophobia and phonophobia

These characteristics will be summarized for each 4-week interval.

Frequency, Change and Percent Change of Migraine Days / Headache Days

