The frequency of migraine days is the number of migraine days within four week intervals and the average four week frequency in twelve and twenty-four week intervals. Change from baseline is the difference in frequency between baseline and the counts within these four week intervals. The 12 and 24 week change is the difference in the frequency between baseline and the average of the 4 week intervals. The percent change is 100 times the ratio of the change and the baseline frequency. Similar measures will be produced based upon headache frequency.

Migraine/ Headache Responder Rate

Three responder rates will be utilized: 50%, 75% and 100%. A responder is a subject who achieves a $\geq 50\%$ reduction, $\geq 75\%$ reduction, or 100% reduction in migraine days, respectively. These reductions will be evaluated by comparing the baseline frequency of migraine days to the migraine frequency in four week intervals. The same analysis will be conducted for headache days.

Results from the four week intervals will be averaged to produce 12 and 24 week responder endpoints. The Weeks 1-4, 5-8, and 9-12 change from baseline measures are averaged, and the average values are compared to baseline. A 75% migraine responder will be a subject who achieves the specified percent reduction in migraine days within these intervals based upon the average change from baseline measures. Specifically, the 75% 12 weeks responder status is defined as,

$$75\% \text{ Responder Status} = \begin{cases} 1 & \text{if } \frac{\text{ave}(\Delta_{\text{Month } 1}, \Delta_{\text{Month } 2}, \Delta_{\text{Month } 3})}{\text{Baseline}} \leq -0.75 \\ 0 & \text{if } \frac{\text{ave}(\Delta_{\text{Month } 1}, \Delta_{\text{Month } 2}, \Delta_{\text{Month } 3})}{\text{Baseline}} > -0.75 \end{cases}$$

A 50% migraine responder will be similarly defined.

The 100% migraine responder rate over Weeks 1-12, 13-24, and 1-24 are calculated by averaging the subjects 100% responder status (i.e. 1 if responder and 0 if not). So a subject who is a 100% responder for month 1 but not 2 and 3 will have a 100% responder rate of 33% (1+0+0/3).

Percentage of Subjects with a Migraine on the Day after Dosing

The percent of subjects with a migraine on the day after dosing will be summarized. For subjects who do not complete the diary on this day the missing data rule outlined in Section 2.7.2 will be used.

Reduction in Migraine Prevalence from Baseline to Week 4

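### The rule for a missing headache end time has no floor at the headache's start and can spread one open headache over several migraine days, and the SAP neither varies it nor counts its use

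*SAP*

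**What the plan says.** The rule is in SAP 2.7.2, under the missing headache end date and time. It has two limbs, and the earlier result applies.

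- First limb: "the headache end date will be set to the earlier of 23:59 on the day before the next reported headache".
- Second limb: 23:59 on the last diary entry, which the SAP explains as "the last evening report or if no evening report was completed after the start of the headache 23:59 on the day the headache started".

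Headaches with missing end "information will be classified as migraines". The stated reason is that most headaches in this population are migraines. No figure is given, and the reason does not bear on duration.

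Three other places matter:

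- SAP 2.2.1 on the diary: "The evening report is completed each trial day whether or not the subject had a headache". Headaches are logged separately as timed events: "Headaches must be entered in order and at the completion of the headache the subject answers questions about the headache".
- SAP 2.2.2 on days: "A migraine day is defined as any day with a headache that meets the chronic migraine definition". The same section allows one attack to produce several migraine days, and it defines migraine hours as summed durations.
- SAP 2.7.3 on sensitivity: the analyses modify Missing Data Rule 2, drop it, move the baseline window, or extend the repeated-measures model to six intervals. All keep the end-time rule. SAP 3.3.7 summarises missing diary days, not headaches without an end. Protocol 13.3.2 has no end-time rule.

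**The concern.** There are two separate weaknesses.

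First, only the second limb falls back to the start day. When the next headache begins on the same calendar date, taking the earlier limb selects the previous midnight, so the headache ends before it begins. Migraine hours then receive a negative term. If migraine days are derived from the start-to-end interval, that headache also contributes no migraine day.

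Second, evening reports continue on headache-free days, so the last diary entry is often no effective cap. One entry that the subject forgot to close can then become migraine on every day until the day before the next headache. If there is no later headache, it runs to the last entry.

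The imputed days feed the primary endpoint, the responder rates and the prevalence endpoints. The responder tests are the more exposed, because a few added days can move a subject across the 75% line. Under SAP 2.3 and Table 2, both 75% responder tests for 300 mg are in the first key secondary group, where one failure stops all later testing, including the 100 mg primary comparison. Without a count of open headaches, nobody could tell afterwards whether the rule mattered.

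**Working it through.** **1. The plan's own power.** Inputs from SAP 1.5: 350 per group, 1-day effect, SD 4, responder rates 20% and 31%; two-sided 5%.

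- Primary: 1 / (4 × √(2/350)) = 3.307, and Φ(3.307 − 1.960) = 0.911.
- 75% responders: pooled rate 0.255, null SE √(2 × 0.255 × 0.745 / 350) = 0.0329, alternative SE √((0.20 × 0.80 + 0.31 × 0.69) / 350) = 0.0327. Φ((0.11 − 1.960 × 0.0329) / 0.0327) = 0.918.

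Both agree with the stated 90%.

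**2. The rule applied literally.**

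| Case | Imputed end | Result |
|---|---|---|
| Start 09:00, next headache 18:00 the same day | 23:59 the day before | −9.02 h |
| Start Day 5, next headache Day 10, daily evening reports | Day 9, 23:59 | 5 migraine days |
| Start Day 60, no later headache, last evening report Day 83 | Day 83, 23:59 | 24 migraine days |
| Start Day 60, no evening report afterwards | Day 60, 23:59 | 1 migraine day |

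**3. Effect on the primary endpoint.** The documents give no rate of open headaches, so a share q is assumed. Also assumed: daily evening reports, at most one headache per day, baseline unaffected, SD held at 4. Take m true migraine days and h headache days per 28. Each headache-free day is imputed if the preceding headache was left open, which adds q(28 − h). Non-migraine headaches reclassified as migraine add q(h − m). The total is q(28 − m). For m = 9 and q = 2% this is 0.02 × 19 = 0.38 day; a simulation gave 0.36 to 0.38.

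With q equal in both arms, a 1-day difference becomes 1 − q:

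| q | Effect (days) | Power |
|---|---|---|
| 0 | 1.00 | 0.911 |
| 1% | 0.99 | 0.906 |
| 2% | 0.98 | 0.900 |

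If q differs by arm, the bias is about the difference in q × (28 − m). For one percentage point this is 0.01 × 22 = 0.22 day at m = 6 and 0.01 × 16 = 0.16 day at m = 12.

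**4. Effect on 75% responders, Weeks 1–12.** Assumed baseline of 16 migraine days, so the cut-off is 4 per 28, or 12 over 84 days. A subject with 3 per 28 has 9 over 84 days and loses the status with 4 or more added days. Simulated with equal weight on 0 to 3 migraine days per 28, and with headache days either equal to migraine days or set at 6, 8 or 10 per 28, the share of true 75% responders lost is 2.6–3.9% at q = 1% and 5.9–7.7% at q = 2%. Scaling both planned rates by (1 − loss):

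| q | Loss | Power, 31% vs 20% before loss |
|---|---|---|
| 0 | none | 0.918 |
| 1% | 2.6–3.9% | 0.903–0.908 |
| 2% | 5.9–7.7% | 0.888–0.895 |

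At 7.7%, for example, the rates are 0.185 and 0.286, and power is 0.888. For Weeks 1–4 at q = 2% the range is 0.892–0.909. Letting the rule act on baseline too (16 migraine and 20 headache days) gave losses of 2.8–3.7% and 6.2–7.3%, so the fixed baseline does not drive the result.

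**The case against.** **Some imputed days would be genuine.** SAP 1 describes episodes as typically lasting 4 to 72 hours, and SAP 2.2.2 allows multi-day attacks. The mean headache-free run after an open headache is (28 − h)/h, which is 1.8 days at h = 10 and 2.5 days at h = 8. With the start day that makes about 2.8 to 3.5 days, close to a long attack. This stands. The responder losses above treat every gap day as false, so within their assumptions they are upper bounds. SAP 1.5 also does not say whether 20% and 31% are rates before or after imputation. If after, no planned power is lost.

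**The same-day case depends on the device.** The documents do not say whether the eDiary accepts a second headache while one is open, and headaches must be entered in order. This makes the case narrow, but does not remove it: the first limb itself presupposes that a later headache can be reported.

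**Some handling exists.** Sites monitor diary compliance (Protocol 10.3), and migraine characteristics are summarised by 4-week interval, which may partly reveal unanswered questions. Neither is a count of open headaches.

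**Stronger readings that do not hold.**

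- A reader might infer that a negative duration makes the headache fail the 30-minute test. It does not: "An episode is a single headache event which lasts at least 30 minutes, as defined by the subject reported start and end time". An open headache has no subject-reported end, and SAP 2.7.2 classes it as a migraine without condition.
- A reader might infer that an open headache always runs to the next one. The last-entry limb can stop it sooner.
- A reader might call the rule simply conservative. That requires equal open rates in the arms, which the documents do not establish.

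**Conclusion.** The point holds in limited form. The missing floor is an error in the rule as written, because it permits an impossible duration, but it arises only when another headache starts on the same date. The spreading of one open headache over later days is a defensible pre-specified choice that nothing in the SAP tests or makes visible.

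The size is unknown. At an assumed 1–2% of headaches left open, equal in both arms, primary power remains about 0.90–0.91 and 75% responder power stays at about 0.89 or above, with bias toward no effect. If open rates differ, bias can go either way at about 0.16–0.22 day per percentage point, against a planned effect of 1 day. The documents do not support the conclusion that the primary result is at risk. This is a minor point, at the lower end of changes worth making.

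**What to change.** **In SAP 2.7.2**, state that the imputed end is never before the headache's start, that an open headache followed by another on the same day ends when that next headache starts, and that the start day of an open headache always counts as a migraine day. Leave the primary rule otherwise unchanged.

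**In SAP 2.7.3**, add two analyses of the primary endpoint and of the 75% and 50% responder endpoints: one that counts only the start day of each open headache, and one that classes open headaches as non-migraine. The second is needed because start-day-only leaves the migraine classification, the q(h − m) part, untested.

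**In the outputs**, report open headaches and imputed days by arm and 4-week interval, including baseline.

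The cost is a few lines of text and derivation code, two sensitivity runs and one table. The drawback is that start-day-only undercounts genuine multi-day attacks. If every open headache truly ran one more day, the undercount is q × h: at q = 2%, 0.20 day with 10 headache days against 0.18 day with 9, a difference of about 0.02 day against active treatment. The non-migraine variant will likewise drop genuine migraines, so both should be read as bounds on the rule's influence.
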